9.4 Analysis Plan for Primary and Secondary Endpoints

The primary endpoint is invasive disease-free survival (IDFS) in patient with basal-like TNBC, which is defined to be time from randomization to the earliest of documented disease recurrence (local, regional and/or distant), invasive contralateral breast cancer, invasive any other second cancer, or death. Cases with incomplete follow up or without adequate disease evaluations will be censored at the date last documented to be free of IDFS events. The secondary endpoints include overall survival (OS) recurrence-free survival (RFS), and incidence of toxicity in basal-like TNBC. The final analysis of IDFS and all secondary endpoints except for OS will be conducted at about 7.5 years after study activation (3.9 years of accrual + 3 years of follow up + 0.5 years of data submission and processing). The final analysis for OS will be conducted at about 10.5 years after study activation (3.9 years of accrual + 6.1 years of follow up + 0.5 years of data collection and cleaning).

The distributions of IDFS, RFS and OS will be estimated using the Kaplan- Meier method(45). For the non-inferiority test, the primary analysis for IDFS will be performed using the RCI method with HR being estimated via stratified Cox proportional hazard model, stratifying on the randomization stratification factors. For the superiority tests of IDFS, OS and RFS, the primary analysis will be performed using stratified log-rank tests, and stratified Cox proportional-hazard models will also be built to estimate the HRs for treatment effect for these efficacy endpoints as a supportive analysis. IDFS, OS and RFS in non-basal like TNBC patients (n=158) and in patients with assay failure (n=35) would be analyzed as an exploratory analysis to examine whether the treatment effect appears similar between the three subsets (basal-like and non-basal like subtype TNBC, and patients with unknown subtype). The treatment-by-basal like subtype interaction would be explored using Cox proportional hazard model in the overall study population. In the multivariable Cox models, known prognostic factors will be included as covariates when appropriate, such as age, race/ethnicity, ECOG performance status, et al. Patients with missing values for covariates will be

excluded from modeling when the proportion of missingness is less than 5% and will be imputed appropriately if the proportion of missingness is $\geq 5\%$.

Toxicity analysis will be conducted in all basal-like TNBC cases receiving at least one dose of chemotherapy (i.e., all treated population). Adverse events will be graded using the National Cancer Institute (NCI) Common Terminology Criteria for Adverse Events (CTCAE) version 4.0. All treatment-emergent and baseline adverse events and hematological/biochemical toxicities based on laboratory measurements will be summarized for patients on each arm. The incidence of deaths and treatment-emergent serious adverse events will be calculated along with exact 95% CI based on binomial distribution and compared between treatment arms using Fisher exact test. Also, the incidence of adverse events leading to discontinuation of chemotherapy and/or withdrawal from the study will be summarized and listed. Toxicity in all patients (including both basal-like and non-basal like patients) will be summarized and compared between treatment arms as well.

The proportion of basal-like TNBC in all screened TNBC patients will be calculated with exact 95% CI based on binomial distribution.

Rev. Add6

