2.2 Secondary Clinical Objectives

- 2.2.1 To evaluate OS and RFS in the two arms in patients with TNBC with residual basal-like disease after neoadjuvant chemotherapy.
- 2.2.2 To characterize the side effects and tolerability of each platinum agent (cisplatin and carboplatin) as well as capecitabine in patients with TNBC with residual disease after neoadjuvant chemotherapy.
- 2.2.3 To identify the rate of basal-like gene expression using PAM50 analysis by digital mRNA quantitation amongst drug-resistant residual TNBC after neoadjuvant chemotherapy.
- 2.2.4 To compare the IDFS in TNBC patients with residual non-basal-like disease after neoadjuvant chemotherapy who are randomized to post-preoperative platinum-based chemotherapy with those who are randomized to capecitabine (exploratory analysis).
- 2.2.5 To assess the difference in health-related quality of life (HRQL) between the platinum based and capecitabine chemotherapy arms.
- 2.2.6 To describe the rate of neurotoxicity over time in the platinum arm, the rate of medication adherence in the capecitabine arm and the rates of amenorrhea in both arms (exploratory).

Rev. Add7

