 - Monitor fluid status - maintain adequate hydration.
 - Assess skin/mucous membranes.
 - Assess for signs of peripheral neuropathy - coordination, sensory loss.
- 8.3.12 References
- Calvert AH, et al. Carboplatin dosage: Prospective evaluation of a simple formula based on renal function. *J Clin Oncol* 1989; 7: 1748-1756.
 - Christian MC. Carboplatin. In: *Principles and Practice of Oncology*, PPO Updates 1989; 3(11): 1-16.

Rev. 6/16
Rev. 9/17
Rev. Add7

9. Statistical Considerations

Three changes are made to the study design in the Amendment #7:

- Basal-like subtype is no longer a stratification factor: Current data (ongoing monitoring) suggest that > 75% of the residual tumors tested thus far are basal subtype. Removing basal-like subtype as a stratification factor will speed up randomization and therefore will improve accrual, also allowing investigators who wish to pursue RT *after* chemotherapy completion to do so (this is particularly important for patients that wish to subsequently enroll in the phase III S1418 protocol). Patients will be randomized to arm B or arm C as long as meeting all eligibility criteria listed in Section 3 and the EA Operations Office receives confirmation of receipt of tumor tissue from EA CBPF. The basal-like subtype status will be identified after randomization, and some patients may have assay failure and their basal-like subtype status will be unknown. We expect about 7% of patients will have assay failure based on data available as of June 24, 2019 (24 out of 365 patients screened have had assay failure). This subgroup of patients with unknown disease subtype will be randomized to arm B or arm C, and they will be analyzed separately from patients with known disease subtypes (basal-like vs. non-basal like) as an exploratory objective of the study. The total sample size is updated (775 vs 750) to reflect the impact of removing basal-like subtype from the stratification factor list (i.e., about 7% of patients randomized will have assay failure) and the observed slightly higher proportion of basal-like disease in the patients (observed vs expected: 78% vs 75%).

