9.2 Study Design

Based on the literature, the benefit of platinum agent therapy in TNBC after NAC, if any, is expected to be predominantly in the basal-like subtype. Hence, the primary population for the primary endpoint is the basal-like subtype in this trial. After screening, tumor tissue will be sent to EA CBPF for molecular profile via PAM50 analysis by digital mRNA quantitation (NanoString) in the residual surgical specimen to identify its molecular subtype. At the time when the trial was developed, we expected at least 75% of the residual post-NAC TNBC screened to fall within the basal-like subtype. Based on data available as of the 2019 Spring DSMC meeting, about 78% of the patients randomized to arms B and C fall in the basal-like subtype. We will use this proportion in the below sample size calculation. In addition, about 7% of patients screened had assay failure and their intrinsic subtype is unknown. We assume 7% of patients will have assay failure in the remaining patients as well.

After EA CBPF sending the confirmation of receipt of tumor tissue to EA Operations Office, all eligible patients will then be randomized according to the permuted block algorithm with a 1:1 randomization ratio to platinum and capecitabine arms. Stratification factors include 1) clinical stage at diagnosis (II or III), 2) residual cancer burden after NAC (1~3 cm or > 3 cm), 3) planned platinum agent (cisplatin or carboplatin), 4) anthracycline exposure in the neoadjuvant setting (yes or no), and 5) administration of radiotherapy (yes or no).

Since platinum is considered less toxic than capecitabine and also platinum is expected to be better than capecitabine on improvement of IDFS in patients with basal-like TNBC, a non-inferiority design with superiority alternative (a hybrid design³³ is preferred for this trial). The primary analysis for the primary endpoint will test the null hypothesis of inferiority of platinum. The sample size would be calculated based on a modest superiority alternative hypothesis. If the hypothesis of inferiority of platinum is rejected in the primary analysis, the secondary hypothesis of no difference vs. superiority of platinum will be tested. Due to the closed testing procedure, no multiple-comparison adjustment is required for the two hypothesis tests³⁴

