With an average annual accrual rate of 144 patients with basal-like TNBC, about 3.9 years of accrual will be needed with an additional 3 years of follow up to reach the expected number of IDFS failures. The final analysis for IDFS comparison in the basal-like TNBC patients is expected to be conducted at about 7.5 years (3.9 years of accrual + 3 years of follow up + 0.5 years of data collection and cleaning) after study activation.

We expect at least 78% of the residual post-NAC TNBC screened to fall within the basal-like subtype within the patients with successful assay, and about 7% of patients will have assay failure. Hence, at least 775 patients ($=562/0.78/0.93$) with residual TNBC at the time of surgery will be enrolled to obtain the 562 patients with basal-like TNBC.

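### Section 9.4 puts failed PAM50 assays in the denominator of the basal-like rate, which lowers the estimate by about 5 to 5.5 points if failure is unrelated to subtype

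*Combined protocol and SAP*

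**What the plan says.** Objective 2.2.3 (Section 2.2) is "To identify the rate of basal-like gene expression using PAM50 analysis by digital mRNA quantitation amongst drug-resistant residual TNBC after neoadjuvant chemotherapy". The one analysis sentence for it is in Section 9.4: "The proportion of basal-like TNBC in all screened TNBC patients will be calculated with exact 95% CI based on binomial distribution". That sentence does not mention assay failure.

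Other parts of the plan do:

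- The opening of Section 9, which describes the Amendment #7 changes, warns that "some patients may have assay failure and their basal-like subtype status will be unknown" and gives the count to June 2019: "24 out of 365 patients screened have had assay failure". It gives the running basal-like rate among tested tumours as more than "75% of the residual tumors tested thus far are basal subtype".
- Section 9.2 repeats that "about 7% of patients screened had assay failure and their intrinsic subtype is unknown", and takes its 78% basal-like figure from patients randomized to arms B and C.
- Section 9.2.1.1 attaches a condition to the 78%: "We expect at least 78% of the residual post-NAC TNBC screened to fall within the basal-like subtype within the patients with successful assay". Assay failure then enters the sample size as a separate factor of 0.93.

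**The concern.** The objective asks how common the basal-like subtype is in residual TNBC. A patient whose assay failed says nothing about that, yet under the Section 9.4 rule each one counts in effect as not basal-like. The reported proportion therefore depends on the laboratory failure rate as well as on biology. It is too low unless none of the failed samples is basal-like.

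The plan makes the needed distinction in Section 9.2.1.1, but only for the sample size. Nothing carries it into Section 9.4.

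What is at stake is the published figure for a descriptive objective, and how readers compare it with other data. Sections 1.2 and 11.1.1 cite 70% basal-like among 89 profiled residual tumours. The choice of denominator alone can decide whether the trial's confidence interval contains that value. No test or decision rests on the estimate.

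**Working it through.** **Inputs.** The basal-like rate among typed tumours is p = 78% (Sections 9.2 and 9.2.1.1), with 75%, the expectation when the trial was developed (Section 9.2), as a lower variant. The failure rate is f = 24/365 = 6.58% (opening of Section 9) or the planning value of 7% (Sections 9.2 and 9.2.1.1). The target of 562 basal-like patients and the total of 775 are from Section 9.2.1.1. The 158 non-basal-like patients are from Sections 9.4 and 9.5.

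**The plan's own figure.** 562/(0.78 × 0.93) = 774.7, rounded up to 775. This reproduces the plan and confirms that the 78% applies to successful assays, with failure handled separately.

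**Size of the shift.** If failure is unrelated to subtype, the share of all screened patients confirmed basal-like is p(1 − f), which falls short of p by p × f.

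| p | f | Rule as written, p(1 − f) | Gap, p × f |
|---|---|---|---|
| 78% | 24/365 | 72.87% | 5.13 points |
| 78% | 7% | 72.54% | 5.46 points |
| 75% | 24/365 | 70.07% | 4.93 points |
| 75% | 7% | 69.75% | 5.25 points |

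**At the planned size** (exact Clopper-Pearson 95% intervals, taking 775 as the number screened). Typed patients number 562 + 158 = 720, which leaves 775 − 720 = 55 unknown (7.1%).

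- As written: 562/775 = 72.5% (69.2% to 75.6%).
- Valid results only: 562/720 = 78.1% (74.9% to 81.0%).

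The estimate under the written rule lies below the lower limit of the valid-result interval. The first interval contains the cited 70% and the second does not.

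**On the June 2019 counts.** The plan gives no basal-like count for the 365 screened patients, so the count here is assumed: 0.78 × 341 valid results ≈ 266.

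- As written: 266/365 = 72.9% (68.0% to 77.4%).
- Valid results only: 266/341 = 78.0% (73.2% to 82.3%).

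With 0.75 × 341 ≈ 256 instead, the figures are 256/365 = 70.1% (65.2% to 74.8%) and 256/341 = 75.1% (70.1% to 79.6%).

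**Without assuming that failure is unrelated to subtype.** With 266 confirmed and 24 failures, the true proportion among the 365 lies between 266/365 = 72.9% and 290/365 = 79.5%. At planned size the limits are 562/775 = 72.5% and (562 + 55)/775 = 79.6%. The written rule reports the lower limit as the estimate.

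**The case against.** The best defence is that Section 9.4 is silent rather than wrong. It names the population, screened rather than randomized, and a statistician might read screened as meaning typed. Section 9.2.1.1 pairs the two ideas, and Section 11.1.2 derives 750 screened patients as 562/0.75 with no allowance for failure. That may have been the intention. But the opening of Section 9 and Section 9.2 both count failures among screened patients, and Section 9.2.1.1 had to add the successful-assay condition explicitly. Section 9.4 has no such condition, so two analysts could report figures about 5 points apart.

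A second point is that Sections 9.4 and 9.5 give 35 patients with assay failure or unknown subtype. That is 4.5% of 775, and the gap would be about 3.4 to 3.6 points. However, 562 + 158 + 35 = 755, not 775, so the 35 conflicts with the plan's own total, which needs 55. Even at 35 the shortfall remains.

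Two further points stand. The illustration on 365 patients uses assumed basal-like counts, so it restates p × f and is not independent evidence. And restricting to valid results is itself unbiased only if failure is unrelated to subtype. The written rule, though, needs the stronger assumption that no failed sample is basal-like.

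**Conclusion.** The concern holds. The denominator stated in Section 9.4 yields the proportion confirmed basal-like, not the rate that objective 2.2.3 asks for. The shortfall is 4.9 to 5.5 points at the plan's failure rates of 6.6% to 7% and basal-like rates of 75% to 78%, provided failure is unrelated to subtype. Without that proviso, the written figure is the lower bound of a range about 7 points wide (72.5% to 79.6% at planned size). Screened patients with no PAM50 result for some other reason would widen the gap; the documents give no count of them.

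The importance is low. One descriptive estimate is affected, and nothing in the primary comparison changes.

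**What to change.** In Section 9.4, define the denominator as screened TNBC patients with a valid PAM50 result, keep the exact 95% interval, and add that the assay-failure proportion will be reported separately among all screened patients. Bounds that count every failed sample first as non-basal-like and then as basal-like can be added, and would show how far the estimate depends on failure being unrelated to subtype.

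The cost is one sentence and no new data. The interval rests on about 7% fewer patients, but its width barely moves: 9.1 points on 341 patients against 9.4 points on 365 in the illustration with 266 basal-like. The change should be made before the final analysis. The plan's 78% comes from randomized patients, so a rate in screened patients will still refer to a somewhat different population.

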9.5 Biomarker Correlative Study

For this correlative biomarker study, we will combine all the patients on all the arms since we don't expect the prognostic value of the biomarkers of interest (i.e., tumor genomic alterations, CTCs) will differ by type of chemotherapy patients received and the intrinsic subtype. The total sample size is 775 patients for EA1131 (562 basal-like patients, 158 non-basal-like patients and 35 patients with unknown subtype). As of June 2019, about 260 patients have enrolled to the study. Taking into consideration of various factors (continuous enrollment in the upcoming months, assay failure, etc.), we expect to have successful genomic profiling of the surgical specimens from at least 400 patients at the end of the study. Per the study protocol, the final analysis of the primary endpoint of the EA1131 trial will take place at 3 years after accrual completion. At the final analyses time (6.9 years after study activation), 196 IDFS events (including recurrence, contralateral breast cancer, second invasive primary cancer, and death) are expected to have occurred to the 562 basal-like TNBC patients based on the alternative hypothesis of the EA1131 study. Of the 196 IDFS events, it is expected that approximately 75% will be recurrence or death, i.e., relapse-free survival (RFS) events. Assuming the same distribution of RFS in the 158 non-basal-like patients and in the 35 patients with unknown subtype, there will be approximately 100 RFS events occurred to the 400 patients with successful genomic profiling, assuming success of genomic profiling is independent of risk of recurrence and basal-like subtype.

9.5.1 Genomic alterations in the surgical specimen

We hypothesize that genomic alternations identified via genomic profiling will predict RFS for patients with TNBC at high risk of recurrence. The frequency of genomic alterations identified will be assessed via genomic profiling in TNBC patients with high risk of recurrence, and associations between genomic alterations and RFS will be assessed; we expect that we can identify some genomic alterations that can predict RFS in TNBC at high risk of recurrence.

With 400 patients and 100 RFS events, for a binary genomic alteration (i.e., the genomic alteration is coded as a binary variable), the minimal hazard ratio (HR) that could be detected with 80% power at two-sided type I error of 0.05 will be 1.78 assuming 50% of the patients have the genomic alteration and the genomic alteration increases risk of recurrence. The minimal HR will be 1.85, 1.75, 1.87 and 2.06 if the proportion of genomic alteration is 20%, 40%, 60% and 70%, respectively.

Frequency of genomic alterations will be summarized using binomial proportions and 95% exact confidence interval. Association of genomic alterations with RFS (i.e., prognostic value of genomic alterations) will be analyzed using log rank test and Cox proportional hazard models. Available potential confounding variables will be adjusted in the Cox model. Due to the exploratory nature of the study, no adjustment will be made for multiple comparisons. All testes will be two-sided with significance level of 0.05. In addition to the prognostic value of genomic alterations, the predictive value of genomic alterations will also be explored via a treatment-by-biomarker interaction test in multivariable Cox proportional hazard models. These analyses will have limited statistical power without prior hypothesis, and they will be considered exploratory and hypothesis generating.

Rev. Add7

9.5.2

Peripheral Blood CTCs

We hypothesize that the detection of CTCs at baseline after completion of protocol therapy will predict RFS for patients with TNBC at high risk of recurrence. Further, we predict that the percent change in CTC from pre to post-therapy will also predict RFS, with lower RFS in those who turn from positive to negative over the course of treatment than those who remain positive or turn positive after treatment.

We will determine the proportion of, and factors associated with CTC detection at baseline in early stage TNBC. We will also assess the proportions of patients whose CTCs disappear or persist after chemotherapy. We will evaluate the association between detection of CTC after completion of chemotherapy and RFS and see whether persistence of CTC after chemotherapy can predict disease recurrence. We will also evaluate the association between change in CTC and RFS to see whether lack of decrease in CTC can predict higher risk of recurrence.

In order to test the hypothesis about CTC and RFS, research blood is mandatory for all patients enrolled in the trial, and all patients with research blood and successful assay results about CTC will be included in the analysis. Of the 400 patients with successful CTC detection at baseline and after completion of chemotherapy, we expect that about 35% of them will have detectable CTCs after completion of adjuvant chemotherapy. CTC detection will be coded as a binary variable (positive versus negative), and presence of CTC is defined as any detectable CTC, e.g., ≥ 1 CTC in 7.5 ml blood. With 100 RFS events at the analysis time (assuming no RFS event before

completion of chemotherapy), the minimal HR for presence of CTC versus absence of CTC that could be detected with 80% power at two-sided type I error of 0.05 will be 1.75. The minimal HR that can be detected with 80% power will be 1.85, 1.80, 1.77, and 1.76 if the proportion of CTC is 20%, 25%, 30% and 45%, respectively.

Associations between detection of CTC at completion of chemotherapy as well as change over the course of therapy and RFS will be analyzed using Cox proportional hazard models. Available potential confounding variables will be adjusted in the Cox models. Landmark method will be used for these analyses with landmark time point at 5 months (i.e., completion of chemotherapy in both arms). Factors associated with CTC detection at baseline will be analyzed using Chi square test and Logistic regression models. Due to the exploratory nature of the study, no adjustment will be made for multiple comparisons. All testes will be two-sided with significance level of 0.05.

Rev. Add7

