2.3 Secondary Correlative Biomarker Objectives

- 2.3.1 To evaluate the association of genomic alterations identified via profiling of the surgical tumor specimen with RFS in patients with TNBC after neoadjuvant chemotherapy.
- 2.3.2 To explore whether any of the genomic alterations identified via profiling of the surgical tumor specimen can predict treatment benefit in patients with basal-like TNBC.
- 2.3.3 To determine the frequency of CTC positivity at baseline and after completion of study therapy in patients with TNBC with residual basal-like disease after neoadjuvant chemotherapy.
- 2.3.4 To evaluate the associations between CTC levels at baseline, and after completion of chemotherapy, with RFS

- 2.3.5 To evaluate the association between CTC change in status post-treatment (i.e. negative to negative, negative to positive, positive to negative, positive to positive) and RFS.
- Rev. Add8 2.3.6 To explore significance of CTC number/phenotype in predicting RFS.
- Rev. Add7 2.4 Exploratory Correlative Biomarker Objectives
- 2.4.1 To determine the frequency of plasma tumor cell-free DNA (cfDNA) positivity at baseline and after completion of study therapy in patients with TNBC with residual basal-like disease after neoadjuvant chemotherapy.
- 2.4.2 To evaluate the associations between plasma tumor cfDNA tumor-specific mutations (baseline and after therapy) with RFS.
- 2.4.3 To explore optimal biomarker combination for RFS prediction.
- Rev. Add#5 2.5 Exploratory Tobacco Use Objectives
- 2.5.1 To determine the effects of tobacco, operationalized as combustible tobacco (1a), other forms of tobacco (1b), and environmental tobacco exposure (ETS) (1c) on provider-reported cancer-treatment toxicity (adverse events (both clinical and hematologic) and dose modifications).
- 2.5.2 To determine the effects of tobacco on patient-reported physical symptoms and psychological symptoms.
- 2.5.3 To examine quitting behaviors and behavioral counseling/support and cessation medication utilization.
- 2.5.4 To explore the effect of tobacco use and exposure on treatment duration, relative dose intensity, and therapeutic benefit.
- NOTE:** Tobacco Use objectives described above are ancillary for the Tobacco Use Assessment project approved by NCI. A combined analysis of the data from the selected ECOG-ACRIN trials is planned. Data collected from the tobacco use assessment in each parent study will not be analyzed and reported in the clinical study report.

Rev. 9/17 3.

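### Section 9.5.1 tests an unstated number of whole-exome alterations against RFS at 0.05 each without multiplicity control, while its detectable hazard ratios apply to one alteration

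*Combined protocol and SAP*

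**What the plan says.** Objective 2.3.1 is "To evaluate the association of genomic alterations identified via profiling of the surgical tumor specimen with RFS". It stands in the list of secondary correlative objectives; Section 2.4 is a separate exploratory list.

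Section 9.5.1 hypothesizes that alterations will predict RFS and adds: "we expect that we can identify some genomic alterations that can predict RFS in TNBC at high risk of recurrence". The association "will be analyzed using log rank test and Cox proportional hazard models". On error control it says "Due to the exploratory nature of the study, no adjustment will be made for multiple comparisons" and "All testes will be two-sided with significance level of 0.05".

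The sensitivity statement begins "With 400 patients and 100 RFS events, for a binary genomic alteration". The minimal hazard ratio at 80% power "will be 1.78 assuming 50% of the patients have the genomic alteration and the genomic alteration increases risk of recurrence". For other prevalences: "The minimal HR will be 1.85, 1.75, 1.87 and 2.06 if the proportion of genomic alteration is 20%, 40%, 60% and 70%, respectively".

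Section 1.7.1 sets the breadth: whole-exome sequencing, with RNA sequencing if feasible, and mutations and copy number changes correlated with RFS. Sections 1.7.1 and 11.2.1 say that the completed profiling will identify more accurately the patients at highest risk. Section 9.5.1 closes by calling its analyses exploratory and hypothesis generating; that sentence comes straight after the treatment-by-biomarker interaction tests.

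**The concern.** A single test at 0.05 has a 5% chance of a false positive. A screen applies that rule to every alteration that enters it, so the expected number of false positives grows with the size of the screen. Section 9.5.1 does not bound that size: it has no gene list, no minimum prevalence, no number of tests, no false discovery rate and no validation step. A reader of the eventual list of prognostic alterations could not tell what share of it to expect by chance.

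The detectable hazard ratios add to this. They describe how well one pre-chosen alteration could be studied, but they stand beside a plan to look through many. At stake is which alterations are reported as prognostic, and so which are carried into later risk models or target selection.

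**Working it through.** **Inputs from Section 9.5.1.** 400 patients, 100 RFS events, 80% power, two-sided 0.05, one binary alteration with prevalence p.

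**Step 1: reproduce the plan's hazard ratios.** Use a Wald test of the log hazard ratio with variance 1/d1 + 1/d0, where d1 and d0 are the events in carriers and non-carriers. Split the 100 events under proportional hazards: S1 = S0^HR and 400p(1 − S1) + 400(1 − p)(1 − S0) = 100. Then solve ln HR = (z for alpha + 0.8416) × sqrt(1/d1 + 1/d0), with z = 1.960 for 0.05.

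| Prevalence | Plan | Recomputed |
|---|---|---|
| 20% | 1.85 | 1.848 |
| 40% | 1.75 | 1.752 |
| 50% | 1.78 | 1.782 |
| 60% | 1.87 | 1.868 |
| 70% | 2.06 | 2.058 |

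The plan's figures are right for one test. Check at 20%: d1 = 29.5, d0 = 70.5, sqrt(1/29.5 + 1/70.5) = 0.219, and exp(2.802 × 0.219) = 1.85.

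**Step 2: false positives when k alterations are tested.** The plan does not give k, so the values below are assumptions. With no true association, the expected number of false positives is 0.05k, whatever the correlation between tests. With independent tests, the chance of at least one is 1 − 0.95^k.

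| k (assumed) | Expected false positives | Chance of at least one |
|---|---|---|
| 10 | 0.5 | 40% |
| 20 | 1 | 64% |
| 59 | 2.95 | 95% |
| 100 | 5 | 99.4% |
| 500 | 25 | about 100% |

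Simulated two-sided tests with equal pairwise correlation give lower chances of at least one. At correlation 0.2 they are 59% for 20 tests and 98% for 100. At correlation 0.5 they are 41% for 20, 78% for 100 and 99.9% for 1,000.

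**Step 3: what a stricter level does to the detectable hazard ratio.** Take a per-test level of 0.001 as an illustration (z = 3.2905) at 20% prevalence. The method of Step 1 gives d1 = 34.0, d0 = 66.0, sqrt(1/34.0 + 1/66.0) = 0.211, and exp(4.132 × 0.211) = 2.39. A simpler split of the events in the ratio p × HR : (1 − p) gives 2.35. So the detectable hazard ratio at 20% prevalence moves from 1.85 to about 2.35–2.4.

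**Step 4: low prevalence.** The plan's table starts at 20%. A 5% floor means 0.05 × 400 = 20 carriers. At that prevalence the method of Step 1 gives a detectable hazard ratio of about 2.5 at 0.05 and about 3.5 at 0.001; the simpler split gives about 2.4 and 3.2.

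**The case against.** The strongest reply is that the plan hides nothing. It says that no adjustment is made and why, it attaches no confirmatory claim to Objective 2.3.1, and nothing found here alters treatment, stopping or the clinical endpoints. The secondary list in Section 2.3 itself contains aims worded as exploration (2.3.2 and 2.3.6), so the word secondary does not make 2.3.1 confirmatory. All of this stands, and it keeps the point to one of analysis and reporting.

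It does not settle the matter. The closing label in Section 9.5.1 attaches most directly to the interaction tests and describes analyses without a prior hypothesis, whereas the prognostic analysis has one. Calling a screen exploratory also does not tell a reader how many of its hits to expect by chance. Section 9.6.1 splits the error rate between only two quality-of-life time points, so the plan applies multiplicity control elsewhere to a far smaller family.

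A reader might infer three stronger things that the documents do not support:

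- **That a false hit is almost certain.** This needs about 59 or more near-independent tests. The number is not stated, and 10 to 20 independent tests give 40% to 64%.
- **That the hypothesis cannot fail, or would count as met by one nominal p-value.** Section 9.5.1 states an expectation and sets no criterion for success.
- **That every RNA-sequencing feature is tested.** RNA sequencing is done only if feasible, and Section 1.7.1 names mutations and copy number as what is correlated with RFS. Section 11.2.1 mentions fusions and expression, but Section 9.5.1 does not list them as separate tests.

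**Conclusion.** The point holds as a low-cost improvement to the analysis. An unbounded family of whole-exome alterations is tested at two-sided 0.05 each with no adjustment, and the stated sensitivity is that of a single test. About 5% of truly null alterations are expected to be declared prognostic. The chance of at least one false declaration is 64%, 95% and 99.4% for 20, 59 and 100 tests. Those chances assume no true association, independent tests and a number of tests that the documents do not give; correlation lowers them but leaves the expected count at 0.05 per test. The quoted hazard ratios of 1.75 to 2.06 need no correction, only a statement of what they describe.

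**What to change.** Before RFS is analysed for this objective, amend Section 9.5.1 as follows:

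1. Define the family of alterations by a minimum prevalence among profiled tumors, chosen without reference to outcome (for example 5%), and report how many alterations enter it.
2. Name one p-value per alteration (log-rank or Cox) for the declaration. Declare prognostic alterations by the Benjamini-Hochberg procedure at a stated false discovery rate (for example 10%), with q-values beside the raw p-values.
3. State that the quoted detectable hazard ratios are for one test. Add an illustrative value at a stricter level, such as about 2.35–2.4 at 20% prevalence and per-test 0.001, against 1.85 at 0.05. Benjamini-Hochberg has no fixed per-test level, so this must be marked as an illustration.

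The 5% and 10% are examples; the documents fix neither. Q-values for the interaction tests are optional, because those tests are already labelled hypothesis generating.

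The cost is analysis wording and some extra output, with no change to sample size or data collection. Fewer alterations will be declared and the detectable hazard ratios will look less favourable, most of all for rare alterations near the floor. The raw p-values stay in the report, so no information is lost.
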